1.3 Study Rationale

There is a need for effective HAND treatment, especially in older adults. A pilot trial is required before embarking on a full-scale study for the following reasons:

Complexity: HAND is a complex condition that has only begun to be addressed psychosocially in controlled settings. We have completed preliminary expert consultation to ensure that: (a) the design of the cognitive remediation group therapy (CRGT) aligns with interventions designed from this modality in other sites and contexts; (b) to determine how appropriate training will be provided to the facilitators of the pilot interventions; and (c) to review the measurement tools to ensure they are the best available for this pilot.

Determining Study Participants & Sample Size: Our entry criteria need to be tested in a pilot study to ensure feasibility and to determine sample size needed for a full-scale trial.

1.4 Potential Risks and Benefits to Human Participants

The proposed research requires participants to attend 10 consecutive weeks of group therapy sessions.

Risks

- Discomfort, anxiety, and/or unease arising from participants disclosing sensitive information about themselves to other participants in a group therapy setting.
- Legal risk regarding the standard limits of confidentiality (i.e., harm to self or other, neglect or abuse of a minor, abuse by a regulated health professional).

Benefits

- Potential to improve coping with HAND
- Potential for participants to make connections with one another for informal support following the therapy session
- Participants will contribute to a feasibility study that, if successful, would be the basis for a larger trial.

2. STUDY OBJECTIVES AND DESIGN

2.1 Overall Study Design

This is a pilot, parallel design, randomized, controlled trial (RCT) that will allocate a sample (n=16) of people (≥ 40 yrs old) aging with HIV who have been diagnosed with MND from St. Michael's Hospital (SMH) in Toronto to either **arm 1**: 10 weekly 3-hour sessions of CRG; or **arm 2**: 10 weekly 3-hour sessions of HIV group therapy.

2.2 Primary Objectives

- Determine if a 10-session CRG is feasible and acceptable to older adults with mild-to-moderate HAND.

Feasibility will be measured based on a sampling frame of approximately 100 people. The following targets (all based on a denominator of 100) would need to be met for a larger study to be considered feasible: $\geq 30\%$ of those contacted agree to participate, $\geq 25\%$ complete the Baseline Visit, $\geq 20\%$ attend the first session, $\geq 16\%$ complete the full series and complete the Follow-up Visit. Each participant must attend 80% (8/10) of the group sessions to be considered as completing the series. Similar targets have been set in other pilot studies of psychosocial interventions (Kazak et al., 2005; Ledderer et al., 2013). These targets are also set to ensure that the study feasibly lead to a larger trial, as support groups require a minimum four participants per session (Stewart, Usher, & Allenby, 2009). There is also a risk to intervention integrity and group cohesion if participants consistently miss multiple sessions, usually defined as more than two sessions in a time-limited program (Stewart, Usher, & Allenby, 2009).

For acceptability, the number of participants in the sampling frame will be reported. Those who consent to participate will be described (i.e., age, gender, ethnicity, length of time living with HIV, length of HAND diagnosis, length of time since last HAND follow-up at St. Michael's Hospital). For those who discontinue participation in the study, the research coordinator will follow-up by phone to ascertain the reason for attrition and this will be described, if the participant agrees. Participants will complete a standardized satisfaction scale (i.e., the Helping Characteristics of Self-Help and Support Groups Measure) that will be complemented by questions about session length, number of sessions, activities used, and evaluation of facilitators.

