Exploratory Objectives	
 1. Change in stress, anxiety, and coping from pretest to posttest (between groups) 2. Sustained use of brain training activities 3. Change in use of mindfulness strategies (between groups)
Sample Size	N = 16
Randomization	1:1 8 in the treatment group and 8 in the active control group
Study Population	HIV-positive people \geq 40 years of age who have been living with HIV for more than 5 years and who have completed neuropsychological testing, received a diagnosis of Mild Neurocognitive Disorder (MND)
Experimental Therapy Description	Cognitive remediation group therapy: 10 weekly 3-hour sessions; each session is comprised of 45 minutes of tablet-based cognitive training using PositScience, a 15-minute break, and 1.75 hours of Mindfulness-Based Stress Reduction (MBSR) with a 15-minute break halfway through the MBSR component.
Active Control	10 weekly 3-hour sessions with a 15-minute break at the end of each hour; each session is comprised of process-oriented facilitation using a mutual aid model (i.e., encouraging peer discussion of effects of HIV, aging, and cognitive impairment to identify and initiate coping strategies).
Duration of Study	Ten weeks
Outcome Measures	
Primary:
 
Feasibility: The sampling frame is approximately 100 people. The following targets (all based on a denominator of 100) would need to be met for a larger study to be considered feasible: $\geq 30\%$ of those contacted agree to participate, $\geq 25\%$ complete the pre-test, $\geq 20\%$ attend the first session, $\geq 16\%$ complete the full series and complete the post-test. Each participant must attend 80% (8/10) of the group sessions to be considered as completing the series.

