3. SELECTION AND ENROLLMENT OF PARTICIPANTS

3.1 Number of Participants

A total of 16 participants (8 in each study arm) will be enrolled.

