3.5 Recruitment and Enrollment Procedures

A list of participants who appear to meet entry criteria (based on their last clinic visit) will be provided to the research coordinator by the St. Michael’s Hospital Neurobehavioral Research Unit. The research coordinator will sequentially contact participants by phone during a Screening Call, starting with those who accessed the clinic most recently. The study and entry criteria will be briefly described by phone and, if the prospective participant is interested, a Screening Visit will be scheduled between the potential participant and the research coordinator. The Screening Visit will involve the research coordinator meeting with the participant to discuss the study and review the informed consent form; if the participant does not consent, the visit will end. If the participant is interested but requests more time to look over the informed consent form with family, friends, or their family doctor, an alternative Screening Visit date can be scheduled. If the potential participant immediately consents to participate in the research study, the research coordinator will obtain the participant’s preferred schedule to attend a 10-week group (i.e., afternoons, evenings), and will then discern the participant’s access to a mobile device (i.e., smartphone or tablet). If a prospective participant does not have a mobile device that the PositScience software could be used on, a mobile device will be provided to the participant for the course of the study (returned at the follow-up visit). Participants will also be asked to self-report any changes that they have noticed in their cognition since their last clinic visit. The consent form will include a section allowing the research coordinator to conduct a chart review, to collect demographic information, health history and medication use to confirm eligibility. Once eligibility has been confirmed, participants will be contacted by the research coordinator to schedule a Baseline Visit. Baseline Visits will be held within the same week, to control for a potential time effect. At the conclusion of the Baseline Visit, the participant will be randomized into one of the two study arms. Participants will have a preliminary meeting with the therapy facilitators to acquaint themselves to the upcoming group prior to the first session. This meeting is described in a section 9.3.2.

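### The feasibility rule cannot be passed as written: it needs 20 people at session 1, but the trial allocates at most 16

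*Combined protocol and SAP*

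**What the plan says.** Section 2.2 gives four feasibility targets: at least 30% agree, 25% complete the Baseline Visit, 20% attend the first session, and 16% complete the series (8 of 10 sessions) and the Follow-up Visit. It introduces them with "The following targets (all based on a denominator of 100) would need to be met for a larger study to be considered feasible". The Synopsis repeats the rule, calling the two assessments pre-test and post-test: "The sampling frame is approximately 100 people. The following targets (all based on a denominator of 100) would need to be met". Section 10.4 reports the primary outcome against the Section 2.2 targets.

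On numbers, Section 2.1 describes a trial "that will allocate a sample (n=16) of people", and Section 3.1 says "A total of 16 participants (8 in each study arm) will be enrolled". Section 10.2 bases the 16 on ideal group size and recruitability. Section 3.7 allows a start with 12 (6 per arm) if required. Section 4.1 rules out replacement once the groups have started.

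On the denominator, the first target is worded "of those contacted agree to participate". Section 3.5 says "The research coordinator will sequentially contact participants by phone during a Screening Call", and Section 10.2.1 describes participation against the total number contacted.

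On randomisation, Section 3.5 says "At the conclusion of the Baseline Visit, the participant will be randomized into one of the two study arms". Section 5.1 and Table 1, footnote 2, place it after enrolment is complete.

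**The concern.** Only allocated people can attend a group session, so the trial's size caps the later targets. If a cap lies below its target, the overall verdict is settled before the first call. A trial that filled every place and lost nobody would still have to be reported as showing that a larger study is not feasible, or the criterion would have to be reinterpreted after the data were seen. Neither is acceptable for a primary outcome that the plan makes the condition for a larger trial.

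The unclear denominator adds to this. Calling is sequential and may stop before the whole frame is reached, so the same data could give different percentages under Section 2.2 and Section 10.2.1.

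**Working it through.** **Inputs.** Denominator 100 and targets 30%, 25%, 20% and 16% (Section 2.2, Synopsis); 16 allocated (Sections 2.1, 3.1, 10.2); minimum start 12 (Section 3.7); no replacement after the groups start (Section 4.1).

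**The plan's own sample sizes.** 2 arms × 8 = 16, and 0.75 × 16 = 12. Both reproduce. There is no power calculation to check.

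**Step 1: targets as head counts.** People needed = target × 100, giving 30, 25, 20 and 16. Shortfall = people needed − most people possible.

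| Target | Needed | Most possible, n = 16 | Shortfall | Most possible, n = 12 | Shortfall |
|---|---|---|---|---|---|
| Complete Baseline (if only those enrolled do so) | 25 | 16 | 9 | 12 | 13 |
| Attend session 1 | 20 | 16 | 4 | 12 | 8 |
| Complete series and Follow-up Visit | 16 | 16 | 0 | 12 | 4 |

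The session-1 row fails at both sizes under perfect attendance. The completion row can be met at n = 16 only by 16 of 16, and cannot be met at n = 12. The agreement target (30) is not strictly capped by 16, because people can agree before enrolment closes.

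**Step 2: what 16 of 16 demands (illustration; assumed rates, independent participants).** Chance = p^16. At p = 0.80, 0.90 and 0.95 this is 2.8%, 18.5% and 44.0%.

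**Step 3: would a contacted denominator rescue the rule?** Largest denominator that still passes = n ÷ target.

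- Session 1: 16 ÷ 0.20 = 80; 12 ÷ 0.20 = 60.
- Baseline, if only those enrolled complete it: 16 ÷ 0.25 = 64; 12 ÷ 0.25 = 48.
- Completion: 16 ÷ 0.16 = 100; 12 ÷ 0.16 = 75.

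These targets become attainable only if calling stops early enough. With a fixed number of places, each further call lowers the ceiling.

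**Step 4: the funnel the targets imply.** 25/30 = 83%, 20/25 = 80%, 16/20 = 80%. This describes a trial with 20 starters and 16 completers, not one with 16 starters.

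**The case against.** The best defence is that the denominator is meant to be the number contacted, as the first target, sequential calling and Section 10.2.1 suggest. Step 3 shows that this could make the rule passable. But Section 2.2 and the Synopsis expressly put every target on 100, so this defence swaps an unreachable rule for an undefined denominator. Treating the frame as only approximately 100 does not help unless it is 80 or smaller.

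A second defence is that 16 was meant as the number of completers. The funnel fits that reading, but Sections 2.1 and 3.1 speak of people allocated and enrolled.

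Three stronger readings are tempting and not supported:

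- A reader might infer that 25 Baseline completers must mean 25 randomised. That follows from Section 3.5 alone. Section 5.1 and Table 1, footnote 2, describe randomisation after enrolment is complete, which does not mechanically exclude a surplus of Baseline completers. No section plans such a surplus, so the Baseline shortfall stands, but conditionally.
- A reader might infer that the pilot can tell the sponsor nothing about a larger trial. Agreement, attendance, reasons for attrition, satisfaction and fidelity are all still described.
- A reader might infer that fewer than four completers in an arm breaches the stated need, "support groups require a minimum four participants per session". That minimum concerns attendance at a session. Someone who misses the completer definition may still have attended most or all sessions.

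It is also fair to say that 12 is a contingency, not the plan.

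**Conclusion.** The point stands and needs correcting before enrolment. Taken literally, the rule must return a negative overall verdict: session 1 falls short by at least 4 people at n = 16 and 8 at n = 12. This uses only the plan's own figures and assumes no rates. Completion has no margin at n = 16 and is unreachable at n = 12. The Baseline shortfall (9 or 13) holds if only those enrolled complete Baseline. The denominator conflict is a separate inconsistency, and the two bases agree only if about 100 people are contacted. What is predetermined is the overall feasibility verdict, not the value of the descriptive results.

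**What to change.** Before enrolment, reconcile Section 2.2, the Synopsis and Sections 3.1, 3.7, 10.2 and 10.2.1 so that every target is attainable at both the planned and the minimum sample size, with one named denominator per target. Align Section 3.5 with Section 5.1 and Table 1 on when randomisation occurs. The choice between two readings is the sponsor's.

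**If 16 is the number randomised**, restate the targets as step proportions from the plan's own funnel:

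- agreed / contacted: at least 30%;
- Baseline completed / agreed: at least 83%;
- attended session 1 / Baseline completers offered a place: at least 80%;
- completed series and Follow-up Visit / attended session 1: at least 80%.

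Leave people turned away only because places are filled out of the later denominators. Report counts by arm, and each proportion with a 95% interval, noting that intervals are approximate if calling stops when places fill and that members of one group may not be independent.

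**If 16 is the number of completers**, say so and restate the sample size. The funnel implies 20 starters (10 per arm), and 25 randomised (12 or 13 per arm) if every Baseline completer is randomised. The minimum start of 12 must then be reset or removed.

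**Cost.** Either route changes the primary criterion and needs a protocol amendment with REB review (Section 11.4). The step version adds no participants but lowers the completion bar from 16. At n = 16, 13 attending (13/16 = 81%) and 11 completing (11/13 = 85%) would pass; at n = 12, 10 attending (10/12 = 83%) and 8 completing (8/10 = 80%) would pass. The exact 95% intervals are wide: 54–96% for 13/16, 55–98% for 11/13, 52–98% for 10/12 and 44–97% for 8/10. The completers version keeps the bar at 16 but needs at least 4 more starters, groups larger than the 8 that Section 10.2 calls ideal, and, if 30% agree, contact with about the whole frame (30 ÷ 0.30 = 100).

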2.3 Secondary Objective

- Determine if a 10-session CRGT can be delivered with fidelity.

To measure fidelity, facilitators of both study arms will submit weekly session reports. These reports will include tick-box lists of the therapy components; use of an average 80% of components listed will be considered as good fidelity. These reports will also include open-ended questions about the sessions, including questions on group dynamics, challenges faced, and detail on activities used. Qualitative reports from each arm will be analyzed by coders familiar with the intervention models.

2.4 Exploratory Objectives

- To evaluate the change in stress, anxiety, and coping.
- Sustained use of brain training activities
- Change in use of mindfulness strategies

3. SELECTION AND ENROLLMENT OF PARTICIPANTS

3.1 Number of Participants

A total of 16 participants (8 in each study arm) will be enrolled.

3.2 Inclusion Criteria

1. Male or female; aged ≥ 40 years
2. Documented HAND diagnosis of Mild Neurocognitive Disorder (MND)
3. ≥ 5 years of HIV infection
4. Provided consent to St. Michael's Hospital to be contacted for future research studies
5. Can feasibly attend 10 weeks of group therapy in downtown Toronto

3.3 Exclusion Criteria

1. Diagnosis of another significant psychiatric diagnosis (i.e., schizophrenia, bipolar disorder, etc.) and/or past traumatic brain injury
2. Documented HAND diagnosis of asymptomatic neurocognitive impairment (ANI) or HIV-associated dementia (HAD)
3. Active intravenous or crystal meth drug use
4. Hospitalization within past 1 month
5. Inability to communicate in English
6. Inability to use a tablet

3.4 Concomitant Alcohol and “Street” Drug Use

Active intravenous drugs and/or crystal meth drug use will exclude potential participants from the study. Drug use will not be actively tested during the study period, however both arms will establish and maintain a 24-hour sobriety norm. Participants may be asked to leave a group session if their substance impairment is negatively effecting the group experience for other participants.

3.5 Recruitment and Enrollment Procedures

A list of participants who appear to meet entry criteria (based on their last clinic visit) will be provided to the research coordinator by the St. Michael’s Hospital Neurobehavioral Research Unit. The research coordinator will sequentially contact participants by phone during a Screening Call, starting with those who accessed the clinic most recently. The study and entry criteria will be briefly described by phone and, if the prospective participant is interested, a Screening Visit will be scheduled between the potential participant and the research coordinator. The Screening Visit will involve the research coordinator meeting with the participant to discuss the study and review the informed consent form; if the participant does not consent, the visit will end. If the participant is interested but requests more time to look over the informed consent form with family, friends, or their family doctor, an alternative Screening Visit date can be scheduled. If the potential participant immediately consents to participate in the research study, the research coordinator will obtain the participant’s preferred schedule to attend a 10-week group (i.e., afternoons, evenings), and will then discern the participant’s access to a mobile device (i.e., smartphone or tablet). If a prospective participant does not have a mobile device that the PositScience software could be used on, a mobile device will be provided to the participant for the course of the study (returned at the follow-up visit). Participants will also be asked to self-report any changes that they have noticed in their cognition since their last clinic visit. The consent form will include a section allowing the research coordinator to conduct a chart review, to collect demographic information, health history and medication use to confirm eligibility. Once eligibility has been confirmed, participants will be contacted by the research coordinator to schedule a Baseline Visit. Baseline Visits will be held within the same week, to control for a potential time effect. At the conclusion of the Baseline Visit, the participant will be randomized into one of the two study arms. Participants will have a preliminary meeting with the therapy facilitators to acquaint themselves to the upcoming group prior to the first session. This meeting is described in a section 9.3.2.

3.6 Co-enrollment guidelines

Co-enrollment in another HAND or mindfulness treatment study is not permitted.

3.7 Sampling and Recruitment

There are approximately 100 people currently in the sampling frame (see Appendix V). This should provide an adequate frame to recruit participants ($n = 16$), especially as there is little other treatment

available for HAND in Toronto (or elsewhere). We will initiate the trial with a minimum of 75% participant enrolment (n = 12, with n = 6 in the Experimental arm and n = 6 in the Active Control arm) if required.

4. WITHDRAWAL OF PARTICIPANTS

4.1 Withdrawal criteria

Investigators may withdraw a participant from the study in the event that:

- a new health condition appears that is suspected to require care or medications prohibited by the protocol
- it is in the participant's best interest according to an Investigator's clinical judgment
- a participant misses two consecutive sessions
- a participant's substance use has become a hindrance to the experience of other participants

Participants may cancel their participation in the study at any time. When participants cancel, they will be asked if they consent to provide a reason for their withdrawal. Participants will not be replaced in this study once the group therapies commence, as replacement could negatively impact group dynamics.

4.2 Procedures for Discontinuation

If a participant withdraws or is removed from the study for any reason prior to the completion of the study, the reason will be recorded on the appropriate case report form (CRF).

5. RANDOMIZATION PROCEDURE

5.1 Randomization

Once enrollment is complete and all participants have consented to take part in the study and been screened for entry criteria, and attended the Screening Visit and Baseline Visit, the research coordinator will contact the CTN to request randomization assignments. Participants will be randomly assigned to one of the two study arms (Arm 1 = Experimental or Arm 2 = Active Control) using random numbers in blocks of size two. Randomization will be performed in a 1:1 fashion to allow for equal numbers of participants in both arms.

6. THERAPY OVERVIEW

6.1 Arm 1: Experimental Therapy

CRGT will be comprised of 10 weekly 3-hour sessions held at Toronto General Hospital and facilitated by an MBSR-certified social worker and a peer (i.e., person aging with HIV). The peer will lead facilitation of the brain training exercise, which will comprise 1/3 of each group session. The brain training exercise will be delivered on tablets using PositScience software by BrainHQ. This software will be downloaded to participants' mobile device (phone or tablet). If a participant does not have a mobile device, a tablet will be provided. This software tailors the participant experience based on deficit domains. Participants will work through activities and support one another through their various strengths and weaknesses. The MBSR-certified practitioner will lead facilitation of the MBSR

component, which will comprise the remaining 2/3 of each group session. MBSR involves various activities such as meditation, breathing exercises, etc. to achieve emotional regulation.

